1 SUMMARY

Full title	FX06 to rescue acute respiratory distress syndrome during Covid-19 pneumonia
Acronym/reference	FX-COVID
Coordinating investigator	[name], PhD Medical-surgical ICU, La Pitié-Salpêtrière Hospital, Paris
Sponsor	Assistance Publique – Hôpitaux de Paris
Scientific justification	
Vascular leakage following endothelial injury, responsible for interstitial and alveolar edema, is a major feature of pathogen induced acute lung injury [1,2]. As acute respiratory distress syndrome (ARDS) due to pandemic Covid-19 is associated with more than 60% mortality [3], controlling vascular leakage may be a major target to decrease the mortality associated with the spreading of the disease in France.
 
FX06, a drug under clinical development containing fibrin-derived peptide beta15-42, is able to stabilize cell-cell interactions, thereby reducing vascular leak and mortality in several animal models, particularly during lipopolysaccharide-induced and dengue hemorrhagic shock [4]. A phase I study was conducted in humans, with no specific adverse event detected with a dose up to 17.5 mg/kg. In a phase II randomized multicentre double-blinded trial in 234 patients suffering from ST+ acute coronary syndrome, FX06 treated patients exhibited a 58% decrease in the early necrotic core zone. Importantly, adverse events were highly comparable between groups, indicating a high safety profile for the drug [5]. Lastly, the drug was used as a salvage therapy in a patient exhibiting a severe ARDS following EBOLA virus infection [6]. Altogether, those data indicate that FX06 is well tolerated in humans and is a potent regulator of vascular leakage.
 
Our team will soon evaluate the efficacy of this drug in controlling vascular hyperpermeability during systemic inflammatory response syndrome following a cardiac arrest, a study founded by the PHRC (AOR19017). Our hypothesis here is that FX06 may decrease pulmonary vascular hyperpermeability during ARDS following SARS-CoV-2 infection, thereby improving gas exchanges and the outcome of infected patients.

Main objective and primary endpoint	
The FX-Covid trial is a prospective, randomized, double-blinded, multicenter, controlled trial, testing the hypothesis that FX06 infusion in conjunction with optimal medical treatment during SARS-CoV-2 induced ARDS reduces pulmonary vascular hyperpermeability at 7 days, compared to optimal medical treatment alone.
 
The primary endpoint will be the change in extravascular lung water index (EVLWi) assessed by transpulmonary thermodilution between Day 1 and Day 7.
 
Transpulmonary thermodilution systems, part of the standard management in ICU, allow a direct evaluation of vascular hyperpermeability in the lungs using thermodilution technique. EVLWi is a reliable parameter,

	independently associated with mortality during ARDS [2].
Secondary objectives and endpoints	
The trial will test also the hypothesis that FX-06 infusion:
 
 - improves mortality at 30 days following randomization - reduces vascular leak (weight, fluid balance, systolic, diastolic, mean blood pressure, heart rate, catecholamine and lactate clearance) - improves pulmonary recovery - improves the evolution of organ failure - reduces the need for hemodynamic support with catecholamines - reduces the need for renal dialysis 
The study will also evaluate the tolerance of FX06, its pharmacokinetic (PK/PD analysis) and immunogenicity.
 
Accordingly, secondary endpoints will be:
 
 • Evolution of daily extravascular lung water index (EVLWi), cardiac index, global end-diastolic volume index, pulmonary vascular permeability index measured by transpulmonary thermodilution during 7 days. • Overall survival at 30 days • Mortality rate in ICU, in hospital • Rate of withdraw or withhold life-sustaining treatments decision at Day 30 • Vascular leak: 
 ○ Daily weight until D7 (% of D1) ○ Daily fluid balance until D7 ○ Evolution of albuminemia until D7 • Pulmonary recovery: 
 ○ Duration of mechanical ventilation (MV) and MV free days at D30 ○ Ventilator-free survival (proportion of participants alive and off invasive mechanical ventilation) at D30 ○ PaO₂/FiO₂ and Murray ARDS severity score over 15 days ○ Evolution of pulmonary SOFA score over 15 days ○ Evolution of radiological Weinberg score over 30 days, analysed by a specialized radiologist, blinded for the treatment group ○ Rate of rescue therapy with VV-ECMO • Evolution of sequential organ failure score (SOFA) and organ failure (one or more SOFA sub-score ≥3) failure free days at D15 • Hemodynamic parameters 
 ○ systolic, diastolic, mean blood pressure, heart rate during 7 days ○ lactate clearance, measured once a day during 7 days ○ catecholamine-free days at D30 • Duration of renal replacement therapy (RRT), and

	
RRT free days at D30
 
 • Nature and frequency of adverse events • Evolution of FX06 concentration from H0 to H1, measured at time 0 (before FX06 application) and after 5, 15, 30, 60 min • PK/PD analysis will be performed from those dosages, with a reduction of EVLWi of more than 30% before and 3 hours after injection as primary PD endpoint at day 2 • Immunogenicity of the drug will be tested at day 7, according to manufacturer's procedure (cf 5.7) 
Exploratory objectives will be:
 
 - To characterize responder patients (defined as patient with a change in extravascular lung water index between D1 and Day 7 after inclusion > 30%) - To study the prognosis (overall mortality) of responder patients (defined as patient with a change in extravascular lung water index between D1 and Day 7 after inclusion > 30%).
Design of the study	Comparative, double-blinded, controlled (1:1), randomized trial, assessing the effect of FX06 infusion on the top of standard of care vs standard of care alone in 2 parallel arms, and multicentric (3 ICUs from three different hospitals).
Population of study participants	Patients admitted in participating ICUs who received mechanical ventilation for SARS-CoV-2 induced acute respiratory distress syndrome (ARDS)
Inclusion criteria	
 1. Age \geq 18 years 2. SARS-CoV-2 induced pneumonia confirmed by a positive PCR test in nasopharyngeal swab or respiratory tract secretions 3. Acute respiratory distress syndrome (ARDS) according to Berlin criteria (bilateral pulmonary infiltrates on frontal chest x-ray, PaO₂/FiO₂ ratio \leq300 mmHg, objective assessment excluding hydrostatic pulmonary edema) 4. Need for endotracheal intubation and mechanical ventilation 5. Informed consent by patient or legal representative. According to the specifications of emergency consent, randomization without the close relative or surrogate consent could be performed. 6. Affiliated to a social security system 7. Highly effective method of contraception and negative highly sensitive pregnancy test, for women of childbearing potential
Exclusion criteria	
 1. Mechanically ventilation for more than 4 days 2. Patient receiving drugs interfering with inflammation: non-steroidal anti-inflammatory drugs, immunoglobulins. 3. Patients receiving chemotherapy, radiotherapy or immunotherapy for malignancy 4. Participation in another interventional clinical trial 5. Pregnant or lactating women 6. Patient moribund on the day of randomization, defined by a SAPS-II score >90

	
 7. Contra-indication for vascular access implantation for transpulmonary thermodilution monitoring 8. Severe or terminal renal insufficiency (creatinine clearance <30 ml/min) 9. Severe hepatic insufficiency (hepatic SOFA score>2) 10. Severe cardiac insufficiency, with left ventricular ejection fraction<30% 11. Any history of severe allergic drug reaction (anaphylactic shock or allergic angioedema) 12. Persons deprived of their liberty by a judicial or administrative decision (guardianship or tutelage measure)
Investigational medicinal product(s)	Development phase IIa FX06 i.v.: 400 mg per day (divided in two injections) during 5 days
Comparator treatment	Equivalent placebo
Interventions added for the study	None other than treatment or placebo injection. Particularly, EVLWI monitoring is part of the routine care of ARDS patients. Chest X-Rays (D15 and D30, only if hospitalized) Phone call at D30 and D60 in case of discharge from the ICU Biological samples for pharmacokinetic study, as well as immunogenicity testing and IL6 dosage
Expected benefits for the participants and for society	Considering the criteria for inclusion, the population included in the trial has a predicted mortality around 60% [3], with severity of vascular leakage associated with mortality [2]. FX06 was able to attenuate vascular leakage in several animal models [4]. It was responsible for a 58% decrease in the MRI evaluated early necrotic zone in a phase II randomized multicentre double-blinded trial conducted in 234 patients suffering from ST+ acute coronary syndrome, without any detectable side effect [5], and successfully rescued a patient with EBOLA-induced ARDS [6]. We therefore believe that the benefit/risk ratio strongly supports the administration of the drug in the study population. More generally, if positive, it will provide a new treatment to decrease the mortality associated with the spreading of SARS-CoV-2 disease worldwide.
Risks and burdens added by the study	Risks due to the treatments D level
Number of participants included	50
Number of centres	5 ICUs in three different hospitals, national setting
Duration of the study	
 - inclusion period: 7 months - participation period (treatment + follow-up): 60days - total duration: 9 months
Number of enrolments expected per site and per month	1,4
Statistical analysis	Analysis will be made with an intent-to-treat design, without interim analysis. The primary endpoint, change of EVLWI from D1 to D7, will be compared between the two groups using analysis of covariance (ANCOVA). For patients dying before 7 days, the last thermodilution data will be retained for the primary analyses. If the patient's

	
condition no longer warrants the presence of the transpulmonary thermodilution systems, then the catheter is removed before 7 days. In this case, the measurement of EVLWi can no longer be made, the last thermodilution data will be retained for the primary analyses. A sensitivity excluding those patients will be performed for analysing the primary endpoint.

Funding sources	
 - MChE Handelsges m.b.H (F4-Pharma), Vienna, Austria, will provide the drug, and participates in the funding of the study - Bouygues SA - Sanofi SA 
None of the investigators has any conflict of interest with this study.

Study will have a Data Safety Monitoring Board	Yes

2 SCIENTIFIC JUSTIFICATION FOR THE STUDY

2.1 Hypothesis for the study

The main hypothesis of FX-Covid trial is that FX-06 may attenuate vascular leakage during SARS-CoV-2 induced acute respiratory distress syndrome (ARDS), with beneficial effects on the outcomes of the patients.

2.2 Description of knowledge relating to the condition in question

Vascular leakage is a major feature of pathogen induced acute lung injury [1,2]. It is triggered by high levels of inflammation in the lungs, due to pathogen-induced endothelial and epithelial lesions. Accordingly extravascular lung water index (EVLWI), a physiological marker of pulmonary vascular leak measured by transpulmonary thermodilution, is independently associated with the outcome of the patients during ARDS [2,7,8]. As ARDS due to COVID-19 infection is associated with more than 60% mortality [3], controlling vascular leakage may be a major target to decrease the mortality associated with the spreading of the disease.

2.3 Summary of relevant pre-clinical experiments and clinical trials

FX-06, a drug arising from research on fibrin-derived peptide B β 15-42, is able to stabilize VE-cadherin dependent cell-cell interactions, thereby reducing vascular leak [9,10]. It was shown to reduce capillary leakage *in vitro* [4] and in several animal models [4,11–13]. It significantly decreased LPS induced pulmonary leakage in rats, and offered a protection from mortality in a model of dengue-virus infection in mice [4].

A randomized placebo-controlled phase I study was conducted in humans, in which no specific adverse event could be detected with a dose escalation up to 17.5 mg/kg [12]. A phase II randomized multicentre double-blinded trial was then conducted in 234 patients suffering from ST+ acute coronary syndrome. FX-06 was injected as a single 400 mg dose at reperfusion. The primary endpoint, which was the infarcted size at day 5 evaluated by late gadolinium enhancement during cardiac MRI, was not statistically different between groups, but patients FX-06 treated exhibited a 58% decrease in the early necrotic core zone, indicating myocardial edema [5]. Importantly, adverse events were highly comparable between groups, indicating a high safety profile for the drug. Lastly, the drug was used with success as a salvage therapy in a patient exhibiting a severe ARDS following EBOLA virus infection [6]. More recently FX06 was used as compassionate therapy in 3 university centers in Germany, in 6 highly severe patients receiving extra-corporeal membrane oxygenation for SARS-CoV-2 disease. The dosage consisted in 400/day during 4 to 7 days. Four over six patients could improve their condition, while 2 died. No clear adverse event related to the treatment could be detected in this cohort (data submitted for publication).

Altogether, those data indicate that FX-06 is well tolerated in humans and is a potent regulator of vascular leakage during ARDS. Our hypothesis here is that FX06 may decrease pulmonary vascular hyperpermeability during ARDS following SARS-CoV-2 infection, thereby improving gas exchanges and the outcome of infected patients.

2.4 Description of the population to be studied and justification for the choice of participants

The population studied will be all patients admitted in one of the participating ICUs exhibiting SARS-CoV-2 induced ARDS and receiving mechanical ventilation.

Justification:

- The mortality of those severe forms of the disease is very high, around 60% [3], justifying an urgent research to find an appropriate treatment.
 - The level of vascular leak is an independent predictor of mortality during ARDS.
-

2.5 Identification and description of the investigational medication or medications

FX06, developed by F4-Pharma GmbH, Vienna, Austria, is an injectable drug arising from research on fibrin-derived peptide B β 15-42. It is able to stabilize VE-cadherin dependent cell-cell interactions, thereby reducing vascular leak.

Concerning tolerance, no specific adverse event could be detected with a dose escalation up to 17.5 mg/kg in a randomized placebo-controlled phase I study in humans [12]. Adverse events were also highly comparable between groups in a phase II randomized multicentre double-blinded trial in patients with ST+ acute coronary artery syndrome [5]. Altogether, these data indicate a high safety profile for the drug.

The dosage will consist in a daily dose of 400 mg/day during 5 days, divided in two injections per day [6].

2.6 Description and justification of the dosage, route of administration, administration schedule and treatment duration

In two other pig models of hemorrhagic shock induced SIRS, one of them with blinding for allocation group, FX06 was responsible for an increased cardiac index and less pulmonary lesions, as indicated by an increase in PaO₂/FiO₂ ratio and a decrease in extra-vascular lung water. FX06 group exhibited also an almost complete abolishment of circulating endotoxemia [13,14]. Doses used in these studies were a single bolus of 2.4 mg/kg at reperfusion [14], and a bolus of 3 mg/kg followed by a continuous infusion of 18 mg/kg/h during 1 hour [13].

In two randomized placebo-controlled phase I studies conducted in humans, no specific adverse event could be detected with a dose escalation up to 17.5 mg/kg [12], and [internal report: *Study FX06AQ-101 [report no. CRO-05-68], First dose in man of FX06, a new peptide preventing inflammation and damage of post-infarction myocardial tissue*]. A phase II randomized multicentre double-blinded trial was then conducted in 234 patients suffering from ST+ acute coronary syndrome. Fx-06 was injected as a single 400 mg dose at reperfusion. The primary end-point, which was the infarcted size at day 5 evaluated by late gadolinium enhancement during cardiac MRI, was not statistically different between groups, but patients FX-06 treated exhibited a 58% decrease in the early necrotic core zone [5]. Importantly, adverse events were highly comparable between groups, indicating a high safety profile for the drug. Lastly, the drug was used as a salvage therapy in a patient exhibiting a severe ARDS following EBOLA virus infection, with a favourable issue. Treatment schedule was a bolus of 400 mg followed by a dose of 200 mg every 12 hrs during 3 days [6]. More recently FX06 was used as compassionate therapy in 3 university centers in Germany, in 6 highly severe patients receiving extra-corporeal membrane oxygenation for SARS-CoV-2 disease. The dosage consisted in 400/day during 4 to 7 days. Four over six patients could improve their condition, while 2 died. No clear adverse event related to the treatment could be detected in this cohort (data submitted for publication). We therefore retained the dosage of 400 mg per day, divided in two injections, and during 5 days, for our study.

2.7 Summary of the known and foreseeable benefits and risks for the research participants

2.7.1 Individual benefit/risk ratio

Considering the criteria for inclusion, the population included in the trial has a predicted mortality around 60% [3], with severity of vascular leakage associated with mortality [2]. FX-06 was able to attenuate vascular leakage in several animal models [4]. It was responsible for a 58% decrease in the MRI evaluated early necrotic zone in a phase II randomized multicentre double-blinded trial conducted in 234 patients suffering from ST+ acute coronary syndrome, without any detectable side effect [5], and successfully rescued a patient with EBOLA-induced ARDS [6]. We therefore believe that the benefit/risk ratio strongly supports the administration of the drug in the study population.

2.7.2 Constraints imposed by the research

Constraints for patients included will be limited (for more details see the section 4, “description of the trial”):

- Administration of the study drug will be made with an IV route, at a time the patients are sedated and equipped routinely with a central venous catheter.
- Recording of clinical parameters and outcome will not differ from usual practice. Particularly, Evaluation of EVLW and other thermodilution parameters using transpulmonary thermodilution technique is part of the standard of care during ARDS [15].
- Biological samples for pharmacokinetic study, as well as immunogenicity testing and IL6 dosage (see 5.7)

3 OBJECTIVES

3.1 Primary objective

The FX-Covid trial is a prospective, randomized, double-blinded, multicenter, controlled trial, testing the hypothesis that FX06 infusion in conjunction with optimal medical treatment during SARS-CoV-2 induced ARDS reduces pulmonary vascular hyperpermeability at 7 days, compared to optimal medical treatment alone.

3.2 Secondary objectives

Secondary objectives will be to test the hypothesis that FX06 infusion:

- improves mortality at 30 days following randomization
- reduces capillary leak (weight, fluid balance, systolic, diastolic, mean blood pressure, heart rate, catecholamine and lactate clearance)
- improves pulmonary recovery
- improves the evolution of organ failure
- reduces the need for hemodynamic support with catecholamines
- reduces the need for renal dialysis

The study will also determine

- the tolerance of FX06
- its pharmacokinetic
- PK/PD parameters of the drug
- Immunogenicity induced by the drug

Exploratory objectives will be:

- To characterize responder patients (defined as patient with a change in extravascular lung water index between D1 and Day 7 after inclusion > 30%)
- To study the prognosis (overall mortality) of responder patients (defined as patient with a change in extravascular lung water index between D1 and Day 7 after inclusion > 30%).

3.3 Objective of any potential ancillary study

Not applicable

4 STUDY DESIGN

4.1 Study endpoints

4.1.1 Primary endpoint

Change in extravascular lung water index (EVLWi) assessed by transpulmonary thermodilution between D1 and Day 7 after inclusion.

Transpulmonary thermodilution systems, part of the standard management in ICU, allow a direct evaluation of vascular hyperpermeability in the lungs. Extra-vascular lung water index (EVLWi) is a reliable parameter, independently associated with mortality during ARDS [2].

4.1.2 Secondary endpoints

- Evolution of daily extravascular lung water index (EVLWi), cardiac index, global end-diastolic volume index, pulmonary vascular permeability index, measured by transpulmonary thermodilution during 7 days.
- Overall survival at 30 days
- Mortality rate in ICU, in hospital
- Rate of withdraw or withhold life-sustaining treatments decision at Day 30
- Vascular leak:
 - Daily weight until D7 (% of D1)
 - Daily fluid balance until D7
 - Evolution of albuminemia until D7
- Pulmonary recovery:
 - Duration of mechanical ventilation (MV) and MV free days at D30
 - Ventilator-free survival (proportion of participants alive and off invasive mechanical ventilation) at D30
 - PaO₂/FiO₂ and Murray ARDS severity score over 15 days
 - Evolution of pulmonary SOFA score over 15 days
 - Evolution of radiological Weinberg score over 30 days, analysed by a specialized radiologist, blinded for the treatment group
 - Rate of rescue therapy with VV-ECMO
- Evolution of daily sequential organ failure score (SOFA) and organ failure (one or more SOFA sub-score ≥3) failure free days at D15
- Hemodynamic parameters
 - systolic, diastolic, mean blood pressure, heart rate twice a day during 7 days
 - lactate clearance, measured once a day during 7 days
 - catecholamine-free days at D30
- Duration of renal replacement therapy (RRT), and RRT free days at D30
- Nature and frequency of adverse events
- Evolution of FX06 concentration from H0 to H1, measured at time 0 (before FX06 application) and after 5, 15, 30, 60 min
- PK/PD analysis will be performed from those dosages, with a reduction of EVLWi of more than 30% before and 3 hours after injection as primary PD endpoint at day 2
- Immunogenicity of the drug will be tested at day 7, according to manufacturer's procedure (cf 5.7)

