5.2.3 D8, D10, D15

- Vital status
- Specific treatment received for SARS-CoV-2 (CTC, Remdesivir)
- Diuretics
- Ventilatory settings:
 - Ventilatory mode (ACV, PSV, APRV, spontaneous breathing)
 - Tidal volume
 - Respiratory rate
 - Positive end-expiratory pressure (PEEP)
 - Plateau pressure
 - FiO₂
- Level of catecholamines: inotrope score, calculated as IS= dose of dobutamine (µg/kg/min)+ 100 x [dose of norepinephrine (µg/kg/min) + dose of epinephrine (µg/kg/min)] [16]
- Biological exams:
 - Arterial blood gases (if clinically indicated)
- Use of renal replacement therapy
- SOFA score
- Chest x-ray (at D15 if clinically indicated)

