5.2.4 Date of ICU discharge or death

- Vital status
 - Specific treatment received for SARS-CoV-2 (CTC, Remdesivir)
 - Diuretics
 - Ventilatory settings:
 - Ventilatory mode (ACV, PSV, APRV, spontaneous breathing)
 - Tidal volume
 - Respiratory rate
 - Positive end-expiratory pressure (PEEP)
 - Plateau pressure
 - FiO₂
 - Level of catecholamines: inotrope score, calculated as IS= dose of dobutamine (µg/kg/min)+ 100 x [dose of norepinephrine (µg/kg/min) + dose of epinephrine (µg/kg/min)] [16]
 - Biological exams:
 - Arterial blood gases
 - Use of renal replacement therapy
 - Chest X-ray if hospitalized and clinically indicated
 - SOFA score
 - Prescription of a highly efficient method of contraception (oral contraception associated with
-

inhibition of ovulation, intrauterine device or hormone releasing system, bilateral tubal occlusion, vasectomized partner or sexual abstinence for more than three months after inclusion), for ICU discharge of women for childbearing potential

5.3 Day 30

- Vital status
- Chest X-ray if hospitalized and clinically indicated
- Rate of withdraw or withhold life-sustaining treatments decision at Day 30
- Duration of mechanical ventilation (MV) and MV free days at D30
- Ventilator-free survival (proportion of participants alive and off invasive mechanical ventilation) at D30
- Secondary ventilator-associated pneumonia, nb of episodes
- Rescue therapy with VV-ECMO
- Catecholamine-free days at D30
- Duration of renal replacement therapy (RRT), and RRT free days at D30
- High sensitive pregnancy test

5.4 Last study visit : Day 60

An additional visit at D60 will be made by investigators by phone, asking to the medical staff in charge of the patient for the patient's status (dead, hospitalized with high-flow oxygen (more than 5 L/min), hospitalized with low-flow oxygen therapy, discharged from hospital). Serious adverse events will be also collected at this time point.

5.5 Expected length of participation and description of the chronology and duration of the study.

Length of Inclusion period 7 months

Duration of participation for each subject, of which:

- Treatment period: 5 days
- Follow-up period with treatment period: 60 days

Total study duration: 9 months

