5.6 Table or diagram summarising the chronology of the study

Actions	D1	D2 to D5	D6 to D7	D8, D10, D15, ICU discharge, death	D30	D60
Information	X					
Signature of the consent form from a close relative or surrogate, or emergency consent form	X					
Randomization	X					
Administration of study drug or placebo	X	X				
Pharmacokinetic study	X					
Medical history	X					
Clinical exam	X					
Co-infection or not	X	X	X			

Weight	X	X	X			
Fluid balance		X	X			
EVLWI measured by TPT (primary endpoint)		X	X			
Standard clinical monitoring	X	X	X			
Ventilatory settings	X	X	X	X		
Doses of catecholamines	X	X	X	X		
Arterial blood gases	X	X	X	X*		
Blood pregnancy test	X				X	
NFS, TP, TCA, fibrinogen, D-Dimers	X	X	X			
Electrolytes, creatinemia, serum glucose, CRP, LDH, NT-pro-BNP, procalcitonin, troponin	X	X	X			
ECG	X	X	X			
Liver tests	X	X	X			
Albuminemia	X	X	X			
SOFA score	X	X	X	X		
RRT or not	X	X	X	X	X	
TTE	X	X	X (D7)			
Chest X-RAY	X	X	X	X*	X*	
Adverse events		X	X	X	X	
Pursuit consent		X	X	X	X	
Vital status					X	
Withhold life-sustaining treatments decision					X	
Ventilator-free survival					X	
Secondary pneumonia, nb of episodes					X	
Rescue therapy with VV-ECMO					X	
Catecholamine-free days at D30					X	
RRT free days at D30					X	
Serum sample for immunogenicity and IL6 measurement			X (D7)			
Prescription of a highly effective method of contraception for three months (for women of childbearing potential)				X (ICU discharge)		
Patient's status						X

*, if clinically indicated

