12 STATISTICAL ASPECTS

12.1 Description of statistical methods to be used including the timetable for the planned interim analyses

The statistical analysis will be performed by a biostatistician of the Clinical Research Unit of Pitié-Salpêtrière Hospital, under the responsibility of [name] [name].

Statistical analyses will be performed with the SAS® or R software with the most recent version at the time of the analysis.

Descriptive analysis will always be overall and by treatment group.

Unless specially mentioned, comparative analysis between groups will be systematically performed without adjustment (univariate analysis);

Flow chart

A flow chart according to the CONSORT recommendations will describe the recruitment and the follow-up of all study population.

Study population

The primary analysis of efficacy endpoints will be performed on all randomized patients for whom a baseline evaluation is available, on an intention-to-treat (ITT) population. All patients will therefore be analyzed in their initial randomization groups.

The safety set is defined as all randomized patients having received at least one dose of study treatment. Safety endpoints will be analyzed on the safety set.

Descriptive analysis

Qualitative variables will be described with frequency and percentage distributions, and quantitative variables with median, interquartile range, minimum and maximum values, mean and standard deviation.

Censored data will be described by Kaplan-Meier estimation or cumulative incidence function, with rate at D7 and D30 with 95% confidence interval.

Baseline characteristics

Demographical, clinical, biological and treatment characteristics will be described.

Primary analysis

The primary analysis will be performed in the intention to treat population.

The primary outcome is the change in EVLWi between D1 and day 7. These changes will be compared between both arms using analysis of covariance (ANCOVA), adjusted for the D1 EVLWi. This is fully equivalent to comparing EVLWi scores at D7 adjusted for the baseline EVLWi. Results will be expressed in terms of adjusted mean changes, with their 95% confidence interval. The unadjusted supportive analysis will be carried out by comparing EVLWi at day 7 between the two arms with a t test.

If the distribution of EVLWi is clearly incompatible with the ANCOVA or t test assumptions, then these analyses will be conducted on the ranks.

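### Organ-failure-free days at D15 cannot be derived from the SOFA schedule as written, and the post-D7 oxygenation and X-ray endpoints rest on conditional or contradictory measurement

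*Protocol*

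**What the plan says.** Section 4.1.2 of the protocol sets these secondary endpoints:

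- "Evolution of daily sequential organ failure score (SOFA) and organ failure (one or more SOFA sub-score ≥3) failure free days at D15". The synopsis has the same endpoint without the word for daily recording.
- "PaO₂/FiO₂ and Murray ARDS severity score over 15 days"
- "Evolution of pulmonary SOFA score over 15 days"
- A radiological Weinberg score followed over 30 days.

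Collection is fixed in section 5:

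- **SOFA** is listed at D1 (5.1), each day D2 to D5 (5.2.1), D6 and D7 (5.2.2), then D8, D10 and D15 (5.2.3), and at ICU discharge or death (5.2.4). Table 5.6 agrees.
- **Laboratory tests.** At D8, D10 and D15 the only biological item is "Arterial blood gases (if clinically indicated". In table 5.6 the rows for blood count, creatinine and liver tests stop at D7. Section 5.2.4 lists blood gases at ICU discharge or death without a condition, but table 5.6 marks that column as conditional.
- **Chest X-ray** is not listed at D8 or D10 in 5.2.3, and is conditional on clinical indication at D15. At ICU discharge or death it is "Chest X-ray if hospitalized and clinically indicated", and 5.3 repeats that condition at D30. The synopsis counts among the study's added interventions "Chest X-Rays (D15 and D30, only if hospitalized", with no clinical-indication condition. Section 5.7 lists no imaging added by the research.

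Section 12.1 compares longitudinal secondary outcomes between arms with a linear mixed model. Section 12.5 says that missing data will be described and that no loss to follow-up is expected.

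**The concern.** A failure-free-day count is a sum over days, and each day needs a yes or no on whether any sub-score reached 3. If the schedule does not produce that answer on a third of the days, the endpoint depends on whatever filling rule is chosen later.

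The oxygenation endpoints have a different problem. When a test is done only if clinically indicated, patients who are improving are less likely to have it. If one arm recovers faster, its later values would come disproportionately from its sicker patients, and a between-arm comparison of measured values could be distorted. Ordinary mixed-model theory covers missingness that depends on values already in the model. It does not cover a decision not to sample that turns on how the patient looks that day. Such values cannot be recovered afterwards, and 12.5 does not anticipate this kind of gap.

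For the Weinberg score, a site cannot tell from the protocol whether the D15 and D30 films are study procedures or depend on routine care.

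**Working it through.** The protocol gives no figure of its own on this point. Its one computed figure, 25 patients per group in section 12.2, concerns the primary endpoint and is not involved. The check is a day count followed by a comparison of passages.

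**1. SOFA days for a patient in ICU through D15**

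- Days needed by the endpoint: D1 to D15 = 15.
- Days scheduled: D1 to D7 (7) + D8 + D10 + D15 (3) = 10.
- Days not scheduled: D9, D11, D12, D13, D14 = 15 − 10 = 5.
- Share missing: 5/15 = 33% of all days, and 5/8 = 62.5% of the days from D8 to D15.

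**2. What that does to the count**

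If *k* of the 10 scheduled days are failure-free, the true number at D15 can be anything from *k* to *k* + 5.

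This takes SOFA at D8, D10 and D15 as fully scorable. The coagulation, liver and renal sub-scores need platelets, bilirubin and creatinine (or urine output), and no blood test other than a conditional blood gas is scheduled on those days. One sub-score of 3 or more is enough to show failure, for example from the recorded catecholamine doses. Showing absence of failure needs all the sub-scores. If routine laboratory results were absent on those three days, the range could widen to *k* to *k* + 8 (15 − 7 = 8).

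**3. Patients who leave ICU or die before D15**

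One further SOFA is recorded at that point. The days after it need a rule, which the protocol does not state. The 5-of-15 figure therefore applies in full only to patients still in ICU at D15.

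**4. Oxygenation endpoints against collection**

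| Endpoint (4.1.2) | Needs | D1–D7 | D8, D10, D15 |
|---|---|---|---|
| PaO₂/FiO₂ over 15 days | blood gas, FiO₂ | both scheduled daily | FiO₂ scheduled, blood gas conditional |
| Murray score over 15 days | PaO₂/FiO₂ among its inputs | scheduled daily | conditional through the blood gas |
| Pulmonary SOFA over 15 days | PaO₂/FiO₂ | scheduled daily | conditional through the blood gas |

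The condition falls on the measured quantity itself.

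**5. X-ray passages for the Weinberg score**

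| Place | D15 | D30 |
|---|---|---|
| Synopsis, added interventions | if hospitalized | if hospitalized |
| 5.2.3 and 5.3 | if clinically indicated | if hospitalized and clinically indicated |
| Table 5.6 | if clinically indicated | if clinically indicated |
| 5.7, added by the research | no imaging | no imaging |

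These statements cannot all hold. Only the synopsis version would give a film for every hospitalized patient.

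**The case against.** The strongest reply is that the gap is narrower than a bare day count suggests. SOFA is also taken at ICU discharge or death, and a simple convention could settle the remaining days. SOFA evolution can be modelled from ten time points, and 15-day follow-up of oxygenation fixes no frequency. Electronic medical records are the source documents (11.3.2), so D9 and D11 to D14 may well be in the charts. How free days are derived between visits is commonly left to a statistical analysis plan. These are also secondary endpoints in a 50-patient phase IIa trial.

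Much of this stands. The discharge or death record does limit the gap, SOFA evolution can be analysed, and nothing here reaches the primary endpoint or the sample size. But an analysis plan can only choose an imputation for days the protocol never asks sites to record. The protocol itself promises a daily score and a count to D15, and its schedule does not deliver them for the patients who stay longest.

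A reader might infer more than the documents support:

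- **That the primary baseline is not collected.** The row "EVLWI measured by TPT (primary endpoint" in table 5.6 has no D1 mark, and 12.1 limits the efficacy population to "all randomized patients for whom a baseline evaluation is available". But 5.1 requires a thermodilution measurement with EVLWi before treatment on D1, and 8.2 has EVLWi recorded from D1 to D7. The empty cell is a clerical mismatch, and nothing suggests that any patient would be lost through it.
- **That the 30-day endpoints fail generally.** Only the Weinberg score is affected. Vital status, ventilator-free survival and the ventilation-, catecholamine- and RRT-free days are all collected at D30.
- **That comparisons should stop at D7 because measurement is complete until then.** Section 12.1 itself provides for death and catheter removal before D7, so completeness through D7 is not assured.

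**Conclusion.** The point holds for secondary endpoints. For a patient in ICU through D15, 5 of 15 SOFA days are not collected, so organ-failure-free days at D15 cannot be derived as written and are uncertain by up to five days. The uncertainty is wider if D8, D10 and D15 cannot be scored from routine laboratory results. This assumes that sites record what section 5 lists and no more.

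For PaO₂/FiO₂, Murray and pulmonary SOFA after D7, missingness depends on patient condition by design. The likely consequence is selection of sicker patients, but the documents give no basis for the size of any bias or for its direction between arms. The Weinberg score rests on passages that contradict each other. The correction is worth making because it is cheap and makes a stated endpoint computable.

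**What to change.** 1. **SOFA.** Record sub-scores and their components from the ICU chart on every day from D8 to D15 while the patient is in ICU. State how days after discharge alive and days after death are counted, including whether failure-free days before a death count. Alternatively, redefine the endpoint to the days actually collected. Align the synopsis with 4.1.2 on daily recording.
2. **Conditional measures.** State that between-arm comparisons of post-D7 blood-gas and X-ray endpoints are supportive and subject to outcome-dependent missingness. Report the number measured per arm and day.
3. **Reconcile passages.** Make the synopsis, 5.2.3, 5.2.4, 5.3, table 5.6 and 5.7 agree on the X-rays, and make 5.2.4 and table 5.6 agree on blood gases at ICU discharge or death. The D1 mark in the EVLWi row can be corrected in the same edit as a clerical matter.

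**Cost:** at most five extra chart-derived SOFA entries (D9, D11 to D14) per patient still in ICU, and the component values on the three days already scheduled. Redefining the endpoint avoids the extra entries but gives up the full 15-day count. The rest is wording, and the sample size does not change.
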